#### Baseline

The “baseline” procedures and data to be collected may be done in one visit or over a series of contacts occurring after the acute VTE event based on information in the patient’s medical record and/or information that is reported by the patient. Treatment with some NOACs (e.g., dabigatran etexilate or edoxaban) requires 5 to 10 days of pre-treatment with parenteral therapy; therefore, additional data will be collected according to the flowcharts (Table [9.3.1:1](#) and [9.3.1:2](#)) at hospital discharge or 14 days after baseline, whichever is later.

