#### Follow-up

Only patients who are treated with dabigatran etexilate or VKA are eligible to participate in the second objective that will include follow-up for up to 12 months after the index event. Balanced enrollment should be followed with regards to the treatment (i.e., dabigatran etexilate or VKA) and the type of index event (e.g., DVT or PE or DVT and PE). The decision to enroll a dabigatran etexilate or VKA patient for follow-up should be made as soon as the dabigatran etexilate or VKA has been prescribed and the patient has signed the study informed consent form (in accordance with local regulations). Patients should not be excluded from participation due to early outcome events (e.g., bleeding events). Data from all visits conducted under usual practice should be recorded in the electronic data capture (EDC) system at each data collection time-point even if the patient stops or changes treatment for the VTE event. Follow-up should be conducted by in-person clinic visits ideally. However, if no follow-up clinic visit occurs as part of clinical practice within one month of the planned data collection time-point (refer to Table [9.3.1:2](#)), then follow-up contact with patient will be done by telephone, and email, if available.

If a patient discontinues the study for any reason, a follow-up assessment should be performed at the time of study discontinuation, if possible.

If the treatment for a patient changes during the study the following guidance should be followed:

- An objective 1 patient whose anticoagulation treatment is switched to DE or VKA can be enrolled into objective 2 as long as inclusion criteria 2 and 4 are met
- An objective 2 patient whose anticoagulant treatment is switched will be followed-up per protocol, including ePROs
- An objective 2 patient who stops taking anticoagulation treatment will be followed-up per protocol but will discontinue ePROs.

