The primary and further outcomes will be analyzed for dabigatran etexilate patients in comparison to VKA patients over 1 year. To support the sample size determination, assessments were performed for the primary safety outcome of major and clinically relevant non-major bleeding based on the observed event rate for VKA in the pooled analysis of the RE-COVER and RE-COVER II trials, and additional assumptions including a 1:1 ratio of dabigatran etexilate and VKA patients, one-year fixed follow-up, one-sided alpha of 0.025, and 15% loss to follow-up (Table [9.5:2](#)). With these assumptions, a total sample size of 5000

patients would provide 90% power to detect a hazard ratio of 0.69 between dabigatran etexilate and VKA.

Table 9.5:2 Sample size assessments for the primary safety outcome of major and clinically relevant non-major bleeding

Event rates		Hazard ratio	Power	Loss to follow-up	Total N
Dabigatran etexilate	VKA*				
5.3%	7.7%	0.69	90%	15%	5000
5.2%	7.7%	0.67			4500
5.1%	7.7%	0.65			4000
4.9%	7.7%	0.63			3500
4.7%	7.7%	0.60			3000

\* The VKA event rate is based on the pooled RE-COVER and RE-COVER II analysis of the oral treatment period [[P13-09153](#), [U12-3306-01](#)]. The Freedman formula was used for the calculations.

In combination with additional non-statistical considerations, a total sample size of up to 5000 patients (i.e., 2,500 patients per group) is deemed appropriate for the planned analyses for [Objective 2](#) on an exploratory basis. The actual power of the analysis will be dependent upon the actual rates of major bleeding and loss to follow-up in the current study, the covariates included in the statistical model, their degree of imbalance between the treatment groups, their strength of association with the outcome, and the use of propensity score matching, and may therefore be different.

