### **9.7.2 Planned analyses**

Analyses will be performed by BI or BI's designees.

The main analysis population will consist of all eligible patients (i.e., all patients who provide informed consent and fulfill all inclusion criteria and no exclusion criteria).

Summary statistics for continuous variables will include the N, mean, standard deviation, minimum, Q1 (lower quartile), median, Q2 (upper quartile), and maximum value; tabulations of categorical variables will include all possible categories and will display the number of observations per category as well as percentages based on the relevant denominators. Estimates from statistical models will be presented with 95% CIs.

Additional details of the planned analysis will be provided in the statistical and epidemiological analysis plan (SEAP).

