7.6 MAIN ANALYSIS

Analyses for the main outcome events are mainly defined for patients in the restricted patient set and, in some occasions for patients in the eligible patient set who took at least once the treatment. In general, recurrent events will be disregarded for the analyses of the outcomes.

Main outcome events – Incidence rates

For the treatment groups incidence rates with 95% CIs, cumulative risks, and KM curves will be calculated on the eligible patient set. Only patients from the eligible patient set that took the prescribed treatment at least once are considered. Patients who complete the planned anticoagulation treatment prior to one year or discontinue initial anticoagulation treatment permanently will be censored at date of last drug intake + 6 days for both DE and VKA or at first intake of another relevant anticoagulation treatment, whichever occurs first. A patient is considered to have permanently stopped initial anticoagulation treatment if other relevant anticoagulation treatment is initiated or if treatment has been interrupted for more than 30 days.

The main analysis of overall incidence rates with 95% confidence intervals, cumulative risks and KM curves will be repeated for the subgroups defined in Section 6.4. A graphical (forest-plot-like) display will additionally be prepared to summarize the subgroup results per outcome on the eligible patient set. Additional subgroup analyses might be conducted as needed.

For all important main and secondary outcomes for patients initiating VKA at baseline, and patients initiating DE at baseline, incidence rates, cumulative risks with 95%-confidence intervals will be calculated by treatment, and for a graphical comparison Kaplan Meier curves

will be plotted. These statistics will be calculated on the restricted patient set, and patients who never took the prescribed treatment will not be included. For the restricted patient set, as a sensitivity analysis, the calculation of incidence rates and cumulative risks will be performed without censoring at permanent discontinuation (intention to treat (ITT) approach). KM curves will be plotted.

Secondary and further outcome events

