Immobilization	True or False (CRF categories, medical history and concomitant diseases will be manually reviewed (past and concomitant))	N/A
Thrombophilia	True or False (CRF categories, medical history and concomitant diseases will be manually reviewed (past and concomitant))	N/A
Pregnancy and peri-partum period	True or False (CRF categories, medical history and concomitant diseases will be manually reviewed (3 month time window))	N/A

Concomitant use of aspirin	True or False (concomitant medication and other VTE therapies will be manually reviewed (concomitant))	N/A
Concomitant use of clopidogrel	True or False (concomitant medication and other VTE therapies will be manually reviewed (concomitant))	N/A
Estrogen therapy	True or False (concomitant medication and other VTE therapies will be manually reviewed (3 month time window))	N/A
Concomitant cancer	True or False (CRF categories, medical history and concomitant diseases will be manually reviewed (concomitant))	N/A
Hypertension	True or False (CRF categories, medical history and concomitant diseases will be manually reviewed (concomitant))	N/A
History of previous VTE	True or False (CRF categories, medical history and concomitant diseases will be manually reviewed (regardless of timing))	N/A
History of major bleeding or prior gastrointestinal bleed	True or False (medical history and concomitant diseases will be manually reviewed (regardless of timing))	N/A
Chronic renal disease	True or False (CRF categories, medical history and concomitant diseases will be manually reviewed (concomitant))	N/A

Patients who complete the planned anticoagulation treatment prior to one year or discontinue initial anticoagulation treatment permanently will be censored at date of last drug intake + 6 days for both dabigatran etexilate and VKA or at first intake of another relevant anticoagulation treatment, whichever occurs first. A patient is considered to have permanently stopped initial anticoagulation treatment if other relevant anticoagulation treatment is initiated or if treatment has been interrupted for more than 30 days.

Multiple imputation methods (e.g. the fully conditional specification method) will be used to impute both continuous and categorical variables appropriately with arbitrary missing patterns.

- b.) In addition, Cox regression analysis (based on the main analysis model) will be performed without censoring at permanent discontinuation (intention to treat (ITT) approach).

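### The SAP analyses labelled intention to treat exclude patients who never took the drug, so events before the first dose, in either arm, enter no visible outcome comparison

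*SAP*

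**What the plan says.** **Protocol.** Section 9.7.2: "The main analysis population will consist of all eligible patients". Membership depends on consent and the entry criteria; intake is not a condition. Section 9.3.2 counts the primary and secondary outcomes from diagnosis of the index event to 12 months after it. Section 9.2.4 (Follow-up) places the decision to enrol at prescription plus consent, and adds: "Patients should not be excluded from participation due to early outcome events (e.g., bleeding events". Section 9.9 (Survivor bias) gives the purpose, which is to capture early events within follow-up. Section 9.7.2.1 makes the primary comparison as treated.

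**Objective 2 SAP.** Section 6.1 assigns groups by prescription but starts follow-up at initiation of the drug. Section 6.3 defines three sets: all eligible, all eligible treated, and restricted. The restricted set comes from a propensity score fitted only in patients with at least one intake, so never-takers are outside it. Section 7.6 says of the restricted-set rates and Kaplan-Meier curves: "These statistics will be calculated on the restricted patient set, and patients who never took the prescribed treatment will not be included". The intention-to-treat versions, for the rates and again for the Cox model in item 2b, use the same wording: the analysis "will be performed without censoring at permanent discontinuation (intention to treat (ITT) approach". Section 4 lists no change from the protocol.

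**The concern.** An intention-to-treat analysis should keep patients in the group they entered, whatever happens afterwards. Here membership depends on something that happens after enrolment, namely taking a first dose. Protocol 9.2.4 (Baseline) says treatment with some newer anticoagulants, DE among them, "requires 5 to 10 days of pre-treatment with parenteral therapy". Enrolment can therefore come before the first dose by several days, early in an acute illness. A bleed, recurrence or death in that interval can be the reason why the drug is never started.

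Two kinds of event are lost. Events in patients who never start leave with the patient. Events before the first dose in patients who do start fall before the SAP's time zero. If the two arms lose different shares of their events, both main outcomes are biased, and the sensitivity analysis that should reveal this has the same gap.

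**Working it through.** **1. The plan's own sizing figure, for scale.** Inputs from Protocol 9.5: "one-sided alpha of 0.025", 1:1 allocation, one-year follow-up, 15% loss, the Freedman formula, and the table row "5.3% 7.7% 0.69 90% 15% 5000" (DE rate, VKA rate, hazard ratio, power, loss, total N).

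- Events needed = (1.960 + 1.282)² × ((1 + 0.69)/(1 − 0.69))² = 10.507 × 29.72 ≈ 312.
- VKA hazard = −ln(1 − 0.077) = 0.0801. DE hazard = 0.69 × 0.0801 = 0.0553. Loss hazard = −ln(0.85) = 0.1625.
- One-year event probability with exponential loss = h/(h + 0.1625) × (1 − exp(−(h + 0.1625))): 0.0711 for VKA and 0.0497 for DE, mean 0.0604.
- N = 312.3/0.0604 ≈ 5,169. An unrounded hazard ratio of 0.685 gives 4,991.
- At N = 5,000: about 302 events and 89.0% power.

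The stated 90% is reproduced to rounding. The point below does not depend on it.

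**2. Who is in each visible outcome analysis (Objective 2 SAP).**

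| Analysis | Patients | At least one intake required? |
|---|---|---|
| Rates and Kaplan-Meier, eligible set (7.6) | eligible | yes, stated |
| Rates and Kaplan-Meier, restricted set (7.6) | restricted | yes, stated |
| Intention-to-treat rates and Kaplan-Meier (7.6) | restricted | yes, by definition of the set |
| Secondary and further outcomes (7.6) | eligible and restricted | yes |
| Overlap-weighted and multivariable Cox (7.6, items 1 and 2a) | restricted | yes |
| Intention-to-treat Cox (7.6, item 2b) | main-analysis model, so restricted | yes |
| Adverse events (7, 7.9.1) | all eligible treated | yes |

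The all eligible set is defined in 6.3, but no visible outcome analysis uses it without the intake condition.

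**3. Time origin.** Protocol 9.3.2, and SAP 5.2 for the secondary outcomes, count from diagnosis. SAP 6.1 counts from first intake. These cannot both hold, and never-takers have no first-intake date.

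**4. What the loss could do.** The documents give no count of never-starters or of pre-intake events. Assumptions for illustration: 2,500 patients per arm, true risk 7.7% in both arms counted from prescription (192.5 events each), and a fraction f of an arm's events lost with patients who never start. The small fall in patients at risk and loss to follow-up are ignored. HR ≈ ln(1 − 0.077(1 − f_DE)) / ln(1 − 0.077(1 − f_VKA)).

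| f | Events removed per arm affected (192.5 f) | DE only | DE f, VKA f/2 | VKA only | Both f |
|---|---|---|---|---|---|
| 2% | 4 | 0.98 | 0.99 | 1.02 | 1.00 |
| 5% | 10 | 0.95 | 0.97 | 1.05 | 1.00 |
| 10% | 19 | 0.90 | 0.95 | 1.12 | 1.00 |

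At f = 10% in one arm, the shift in log HR is about 0.110. The standard error is 2/√(192.5 + 173.25) = 0.105, so the shift is about one standard error, in either direction.

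**5. Power.** If 1%, 2% or 5% of patients never start, N falls to 4,950, 4,900 or 4,750, and power to 88.7%, 88.4% or 87.4%, against 89.0%. Precision is not the issue.

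**The case against.** **The protocol speaks of treated patients.** Section 9.2.4 limits Objective 2 to patients treated with DE or VKA, and 9.7.2.1 bases the primary comparison on treatment actually received. An intake condition implements that. This stands for the main analysis, which should be left alone. It does not justify an intention-to-treat analysis with the same condition. The rule on early events does concern participation rather than analysis sets, but its purpose in 9.9 is defeated if the enrolled patient is then dropped.

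**The SAP explains its own label and reports set sizes by arm.** Both are true. A reader can find how many never-takers each arm has, but not their outcomes.

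**The group may be small.** Enrolment is allowed up to 30 days after diagnosis, and assignment also draws on the prescription at discharge or day 14. Many patients will have started by then. This limits the likely size, but nothing in the plan measures it.

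**Not everything is visible.** Protocol 9.7.2.2 and SAP 5.3, 6.4 and 7.7 are not in the public text. The point is therefore limited to visible analyses.

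**A stronger reading is tempting.** A reader might infer that mainly DE patients are lost, so that the plan favours DE. The documents do not support this. Protocol 7.2 (Treatment Options) places VKA as well as DE after parenteral treatment, and the footnote to Table 6.1:1 of the Objective 1 SAP lists heparin pre-treatment as required for both.

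A reader might also subtract assumed lead-in events from the planned DE rate. With 1.5% of patients having an event and half of those never starting, 0.75 points are lost, and 0.69 × (1 − 0.75/5.3) = 0.59. That calculation sets VKA loss to zero. It also removes events that were never in the 5.3%: the VKA rate of 7.7% comes from the oral treatment period of the pooled trials, and 5.3% is 7.7% × 0.69.

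**Conclusion.** The point holds as a mismatch between the protocol and the SAP. Visible outcome analyses, including both labelled intention to treat, are conditional on intake and start at intake, while the protocol's population is all eligible patients and its outcome window opens at diagnosis. SAP Section 4 does not record this.

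Direction and size are unknown. They depend on counts of never-starters and pre-intake events by arm, which the documents do not give. Under the assumptions shown, the shift is nil when both arms lose the same share of events and about one standard error of log HR when one arm alone loses 10%. No claim that the plan favours DE, or VKA, follows from the documents. The main as-treated analysis remains defensible. What is missing is any visible analysis that could show whether the selection matters, so this should be changed.

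**What to change.** - Keep the as-treated main analysis as it is.
- Run the intention-to-treat sensitivity analyses (the rates in 7.6 and item 2b) on the all eligible set, by drug prescribed at enrolment, with never-takers included.
- State a time origin that does not depend on intake: the prescription or enrolment date, or diagnosis as in Protocol 9.3.2 with delayed entry for time before enrolment. Follow patients to 12 months after diagnosis.
- Refit the propensity score and overlap weights on that set. SAP 6.7 takes covariates up to the start of DE or VKA, so a cut-off is also needed for patients without a start date.
- Tabulate never-takers, and outcome events before first intake, by prescribed drug. The table should also show events before enrolment, which a delayed-entry model would leave out.
- Rename the current run as treated patients without censoring at discontinuation, and record the departure from the protocol's population and outcome window in SAP Section 4.

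The cost is SAP wording, one table, one further propensity-score fit with its weighted Cox run, and the matching rates. The downside is that the intention-to-treat estimate will include a few patients never exposed to either drug.

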For the further outcome events such as Recurrent DVT and/or PE, VTE-related mortality, All-cause mortality, Life-threatening bleeding events, Acute coronary syndrome, and Net clinical benefit, incidence rates, KM estimates and KM curves will be calculated for the eligible patients who took the prescribed treatment at least once for both treatment groups. Additionally, above analyses will be performed on the restricted patient set.

Technical specifications

Incidence rates per 100 patient years with 95%-confidence intervals for important outcome events (single and composite outcome) will be calculated the following way. In addition, these analyses will be done stratified by ongoing chronic antiplatelet treatment at baseline. Recurrent events will be disregarded for calculation of incidence rates. Incidence rate λ is defined as

$$\begin{aligned} \text{Incidence rate } \lambda \left[\frac{1}{100} \text{ pt. yrs} \right]: \\ = 100 * \frac{\text{number of patients with event}}{\frac{1}{365.25} * \sum_{\text{patients}} \text{person time at risk(event)}[\text{days}]} \end{aligned}$$

where the denominator is the patient years under risk. The 2-sided 95% CI of λ will be calculated based on the Poisson distribution and its relationship with the Chi-square distribution according to the following formula [7]

$$[\lambda_{\text{lower}}, \lambda_{\text{upper}}] = [\{0.5 \chi^2(\alpha/2; 2x)\}/n, \{0.5 \chi^2(1 - \alpha/2; 2x + 2)\}/n],$$

where $\chi^2(\gamma, r)$ is the 100 γ th the percentile of a chi-square distribution with r degrees of freedom, n is the patient years under risk for the event, x is the number of patients with event, and α for $(1 - \alpha)\%$ 2-sided CIs.

Cumulative risk is defined as cumulative proportion of patients with event and will be calculated as the Kaplan-Meier estimate for failure. The Kaplan-Meier curve will be plotted. The proportion of patients with event, as well as the proportion of censored patients falling into specified intervals and the Kaplan-Meier estimate for failure will be computed for the following categories:

- ≤ 3 months
- $3 <$ and ≤ 6 months
- $6 <$ and ≤ 12 months
- > 12 months

Distribution and overlap of the ePS between the two groups

The ePS is the probability of a patient being in one of the two treatment groups, conditional on relevant observed baseline variables. For this analysis, the ePS for being in the DE group vs. VKA group will be estimated using the multivariable logistic regression model.

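### The incidence rate is defined per 100 patient-years, but its 95% CI formula has no factor of 100, so the limits come out 100 times too small

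*SAP*

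**What the plan says.** The Objective 2 SEAP, section 7.6, sets out the rate calculation under Technical specifications. It opens: "Incidence rates per 100 patient years with 95%-confidence intervals for important outcome events (single and composite outcome) will be calculated the following way". The rate λ is then defined as 100 times the number of patients with an event, divided by summed days at risk over 365.25, "where the denominator is the patient years under risk".

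The two-sided 95% interval is stated to be for that same λ. It uses the Poisson/chi-square relationship:

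- lower limit: 0.5 χ²(α/2; 2x) / n
- upper limit: 0.5 χ²(1 − α/2; 2x + 2) / n

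The terms are explained as follows: "n is the patient years under risk for the event, x is the number of patients with event".

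Section 7.6 applies rate intervals widely. For the main outcomes, "overall incidence rates with 95% confidence intervals, cumulative risks and KM curves will be repeated for the subgroups defined in Section 6.4". The Technical specifications add: "In addition, these analyses will be done stratified by ongoing chronic antiplatelet treatment at baseline".

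**The concern.** The estimate and its interval are defined next to each other, for the same quantity, with the same denominator. Only the estimate is multiplied by 100. A program that follows the text literally would report a rate per 100 patient-years beside limits per 1 patient-year.

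This is the SEAP's only interval formula for incidence rates, so the slip reaches every rate interval the plan calls for: bleeding, recurrent VTE and the other outcomes, the subgroups, and the antiplatelet strata. The protocol (section 9.7.1) describes the analyses as descriptive and uses confidence intervals for exploration, so these intervals are a substantive part of what will be reported.

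**Working it through.** **Inputs, all from SEAP Objective 2, section 7.6, unless noted**

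- Rate: λ = 100 × x / n, with x = patients with event and n = patient-years at risk.
- Limits as written: L = 0.5 χ²(0.025; 2x) / n (taken as 0 when x = 0) and U = 0.5 χ²(0.975; 2x + 2) / n, with the same x and n.
- The SEAP gives no event counts or person-time, so the values of x and n below are assumptions.
- For the planning example, protocol section 9.5 gives 2,500 patients per group, 15% loss to follow-up and a 7.7% VKA event rate. I assume that lost patients contribute no time and all others one full year: 2500 × 0.85 = 2125 patient-years, and 2125 × 0.077 = 163.6, rounded to 164 events.

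**Step 1: what the formula estimates.** L and U are the exact Poisson limits for a count of x, divided by n. They are limits for x / n, the rate per 1 patient-year. Evaluating the Poisson tail probabilities at these limits gives 0.025 on each side, so the method is sound on that scale. Because λ = 100 × (x / n), its limits are 100 × L and 100 × U. The discrepancy is a factor of exactly 100 for any x and n.

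**Step 2: one case in full.** Take x = 100 and n = 2000.

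- λ = 100 × 100 / 2000 = 5.0 per 100 patient-years.
- L = 0.5 χ²(0.025; 200) / 2000 = 0.0407.
- U = 0.5 χ²(0.975; 202) / 2000 = 0.0608.
- Multiplied by 100: 4.07 to 6.08.

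**Step 3: further cases**

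| x | n (patient-years) | λ per 100 PY | Limits from the formula as written | Limits × 100 |
|---|---|---|---|---|
| 100 | 2000 | 5.0 | 0.041 to 0.061 | 4.07 to 6.08 |
| 164 (planning figures) | 2125 | 7.72 | 0.066 to 0.090 | 6.58 to 8.99 |
| 10 | 500 | 2.00 | 0.0096 to 0.0368 | 0.96 to 3.68 |
| 1 | 2000 | 0.05 | 0.0000127 to 0.0028 | 0.0013 to 0.279 |
| 0 | 2000 | 0 | 0 to 0.0018 | 0 to 0.184 |

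**Step 4: does the interval ever contain its estimate?** The ratio of the upper limit as written to the estimate is U / λ = 0.5 χ²(0.975; 2x + 2) / (100x), which does not depend on n. At x = 1 it is 0.0557. Evaluated for x from 1 to 5000, that is its maximum. The upper limit is thus never more than about 5.6% of the estimate, and the interval excludes its own estimate whenever there is an event. With x = 0 the interval contains 0, so nothing looks wrong, although the upper limit is understated 100-fold.

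**Step 5: what is not touched.** For cumulative risk the SEAP says: "Cumulative risk is defined as cumulative proportion of patients with event and will be calculated as the Kaplan-Meier estimate for failure". That calculation does not use the rate formula. Nor do the overlap-weighted Cox models or the sample size calculation in protocol section 9.5.

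**The case against.** The strongest reply is that only a unit conversion was left unwritten. The opening sentence of the specification fixes the reporting unit for both rate and interval as per 100 patient-years, and the chi-square expression is a correct exact interval per patient-year. A competent programmer would rescale. If not, an interval lying wholly below its own estimate would be noticed in the output. The comparative conclusions rest on the Cox models, which are unaffected. This stands as an argument about practical severity, except that the zero-event case would not reveal itself. It does not make the formula right: the worded definition of n means plain patient-years, which rules out the one reading that would reconcile the two expressions. The same wording makes a symbol lost in PDF extraction an unlikely explanation.

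Two narrower points are fair:

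- **Scope.** For further outcomes such as life-threatening bleeding, acute coronary syndrome and net clinical benefit, the SEAP sentence listing the analyses names incidence rates without naming an interval. These outcomes are reached only through the general specification for important outcome events, and the text does not define which those are. The subgroup definitions in section 6.4 are not in the available text, so the number of affected subgroup intervals cannot be counted.
- **The planning example.** The SEAP censors at last intake plus 6 days or at a switch, and Objective 2 requires only 3 months of planned therapy, so real person-time could be well below 2125 years. The 7.7% also comes from the oral treatment period of the pooled trials. The example shows scale and is not a forecast; the factor of 100 does not depend on it.

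**Conclusion.** The concern holds. As written, the 95% limits for every incidence rate are exactly 100 times too small for the rate they accompany. This follows from the SEAP's own definitions of λ, x and n and needs no assumption about event counts; the numerical examples only illustrate it.

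The finding concerns the written specification. The documents show no program and no output, so whether the error reached any result is unknown. The intended scale is plain and the underlying method is correct. It should be corrected because following the formula literally gives wrong error bars, but it does not threaten the comparative analysis.

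**What to change.** Multiply both limits by 100 in the formula, or redefine n as patient-years at risk divided by 100. Then confirm that the analysis program reports each rate and its interval on the same scale, and check a zero-event cell specifically, since that is where a mismatch would not show. While editing the sentence, change the confidence level from (1 − α)% to 100(1 − α)%.

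The cost is one formula line and one program check, with no new data or analysis.
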